### Other UDAECs are defined as follow:

### Ocular events

The grouping of "ocular events" includes all MedDRA preferred terms under the SOC of "eye disorder" regardless of primary or secondary SOC.

### Anaemia

Anaemia will be analyzed by BI customized medical query (BIcMQ) of Decreased haemoglobin and anaemia (incl. non-haematological causes), as defined in Table 7.8.1: 2

In addition, Standardised MedDRA Query (SMQ) of Haematopoietic cytopenias will be analyzed.

Table 7.8.1: 2 MedDRA preferred terms for BIcMQ of Decreased haemoglobin and anaemia (incl. non-haematological causes)

User-defined AE category	MedDRA preferred terms		
Decreased haemoglobin and	Anaemia	Haemoglobin abnormal	
anaemia (incl. non-	Anaemia Heinz body	Haemoglobin decreased	
haematological causes)	Anaemia folate deficiency	Haemolytic anaemia	
	Anaemia macrocytic	Haemolytic anaemia enzyme specific	
	Anaemia megaloblastic	Haemolytic icteroanaemia	

Anaemia of chronic disease	Hyperchromic anaemia
Anaemia of malignant disease	Hypochromic anaemia
Anaemia postoperative	Hypoplastic anaemia
Anaemia splenic	Iron deficiency anaemia
Anaemia vitamin B12 deficiency	Leukoerythroblastic anaemia
Anaemia vitamin B6 deficiency	Macrocytosis
Anaemic hypoxia	Melanaemia
Anaemic retinopathy	Microangiopathic haemolytic anaemia
Aplasia pure red cell	Microcytic anaemia
Aplastic anaemia	Nephrogenic anaemia
Autoimmune anaemia	Normochromic anaemia
Autoimmune aplastic anaemia	Normochromic normocytic anaemia
Autoimmune haemolytic anaemia	Normocytic anaemia
Blood loss anaemia	Pernicious anaemia
Cardiac haemolytic anaemia	Proerythroblast count abnormal
Cold type haemolytic anaemia	Proerythroblast count decreased
Coombs negative haemolytic anaemia	Protein deficiency anaemia
Coombs positive haemolytic anaemia	Radiation anaemia
Copper deficiency anaemia	Red blood cell abnormality
Deficiency anaemia	Red blood cell count abnormal
Dilutional anaemia	Red blood cell count decreased
Erythroblast count abnormal	Reticulocyte count abnormal
Erythroblast count decreased	Reticulocyte count decreased
Erythroid dysplasia	Reticulocyte percentage decreased
Erythroid maturation arrest	Reticulocytopenia
Erythropenia	Scorbutic anaemia
Erythropoiesis abnormal	Sideroblastic anaemia
Erythropoietin deficiency anaemia	Spherocytic anaemia
Haematocrit abnormal	Spur cell anaemia
Haematocrit decreased	Warm autoimmune haemolytic anaemia

### **Drowsiness**

Drowsiness will be analyzed by a customized query defined in Table 7.8.1: 3.

Table 7.8.1: 3 MedDRA preferred terms for user-defined AE category of Drowsiness

User-defined AE category	MedDRA preferred terms	Scope
Drowsiness	Depressed level of consciousness	Narrow
	Post-injection delirium sedation syndrome	Narrow
	Radiation somnolence syndrome	Narrow
	Sedation	Narrow
	Altered state of consciousness	Broad
	Brain fog	Broad
	Concussion	Broad
	Consciousness fluctuating	Broad
	Intracranial hypotension	Broad
	Lethargy	Broad
	Obstructive sleep apnoea syndrome	Broad
	Orexin deficiency	Broad
	Pickwickian syndrome	Broad
	Post concussion syndrome	Broad
	Presyncope	Broad
	Sedation complication	Broad
	Sleep-related hypoventilation	Broad
	Shift work disorder	Broad
	Sleep apnoea syndrome	Broad

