Iclepertin is primarily metabolized by hepatic CYP3A and clinical drug-drug interaction (DDI) studies were conducted.

Human exposure to Iclepertin up to the no-observed-adverse-effect level (NOAEL) exposure in the most sensitive species (minipig, maximum measured plasma concentration [C_{max}] 1430 nM and area under the concentration-time curve [AUC0-24 h] 26500 nM·h) is considered safe. The 10 mg dose to be tested in Phase III is below the no-observed adverse-effect level (NOAEL) with multiple exposures at 10 mg in humans 6-7x below the NOAEL.

Page 19 of 112

Proprietary confidential information © 2023 Boehringer Ingelheim International GmbH or one or more of its affiliated companies

Data from clinical studies

To date, Iclepertin has been well tolerated and has demonstrated a good safety profile. A total of 323 healthy subjects have received ≥1 dose of Iclepertin. In addition, 339 patients with schizophrenia and 490 patients with Alzheimer's disease (AD) have been treated with Iclepertin for 12 weeks. The most frequent AEs were related to the central nervous system (CNS), with headaches being the most common and more frequent in the active groups than in placebo groups. Dizziness, somnolence and gastrointestinal disorders, such as nausea and vomiting, were also among the AEs reported more frequently on Iclepertin than placebo.

Phase II trials of 12-week treatment duration in patients with schizophrenia and Alzheimer's disease, like trials with other GlyT1 inhibitors such as bitopertin [R15-1266, R18-1054], detected an impact of Iclepertin on haemoglobin (Hb) levels. There was a slight decrease in Hb across the active treatment groups, compared to placebo. It should be however noted that majority of patients (over 90%) remained in the range of normal values.

There were no other clinically relevant findings in the clinical laboratory evaluation, 12-lead electrocardiograms (ECG), assessment of vital signs, or visual tests. No signal was observed for suicidal ideation or behaviour.

Page 20 of 112

Proprietary confidential information © 2023 Boehringer Ingelheim International GmbH or one or more of its affiliated companies

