The most frequent AEs were CNS-related • Headache-reversible and can be clinically monitored.	These effects are understood to be typically mild to moderate and transient. Refer to IB for more details.	Management of symptoms, evaluation, and follow-up as needed to ensure patient safety, per investigators clinical judgment.
• Somnolence (drowsiness)		
Decrease in Hb	 GLYT1 is present on erythrocyte precursors in the bone marrow and on circulating reticulocytes and glycine is required for Hb synthesis. No clear decrease in Hb was seen in Iclepertin-treated subjects compared to placebo in phase I. In phase II, the mean decrease in Hb was observed for 10 mg and 25 mg compared to placebo [10 mg: -3.3 g/L (-0.33 g/dL); 25 mg: -4.5 g/L (-0.45 g/dL); placebo: -0.5 g/L (0.05g/dL)] 	 Patients with Hb below lower limit of normal at Visit 1 assessed by the central lab will be excluded from participation in this study. For other GLYT1 inhibitors maximum decrease in Hb was observed after 4 months of treatment, Hb will be checked at Visit 9. Please refer to section 5.2.6.4 for more details.

Page 23 of 112

Proprietary confidential information © 2023 Boehringer Ingelheim International GmbH or one or more of its affiliated companies

Table 1.4.2:1 Overview over trial related risks (con't)

Possible or known risks of clinical relevance for this trial	Summary of data, rationale for the risk	Mitigation strategy
Investigational Med	licinal Product	
Ocular AEs	The ocular safety of Iclepertin and its effects on ophthalmologic physiology in patient with schizophrenia were characterised in an ocular substudy as part of trial 1346-0009, in which a subset of patients underwent special ocular safety assessments. No meaningful changes from baseline or differences between Iclepertin treatment groups and placebo were observed with regards to the analysed ocular safety variables.	Ocular AE will be monitored and followed up per investigators judgment (refer to Section 5.2.6.3). Verbatim description for each ocular AE is needed For ocular the patients must be sent to an ophthalmologist for detailed evaluation. Report from the ophthalmology examination will need to be collected.
BI425809- Drug In	teractions	

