#### 7.8.1 Adverse events

Unless otherwise specified, the analyses of AEs will be descriptive in nature. All analyses of AEs will be based on the number of subjects with AEs and not on the number of AEs. The reporting and analyses of AEs will follow the BI guideline (3). AEs will be coded with the most current version of MedDRA®.

For further details on summarization of AE data, please refer to (1, 3).

The analysis of AEs will be based on the concept of treatment emergent AEs. That means that all AEs occurring between the date of the first administration of trial treatment till the date of the last administration of trial treatment + residual effect period will be assigned to the ontreatment period. All AEs occurring before the first administration of trial treatment will be assigned to 'screening' and all AEs occurring after the residual effect period will be assigned to 'follow-up'. For details on the treatment definition, see Section 6.1.

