### Sleep disorder

Sleep disorder related AE search terms are based upon the FDA Medical Queries (FMQs) of Insomnia (broad) and Somnolence (broad). Refer to Table 7.8.1: 4 for a list of MedDRA preferred terms in each of the groupings.

Table 7.8.1: 4 MedDRA preferred terms for user-defined AE categories of sleep disorder AEs

User-defined AE category	MedDRA preferred terms		
FMQ Insomnia (broad)	Advanced sleep phase	Primary insomnia	
	Behavioural induced insufficient sleep syndrome	Psychophysiologic insomnia	
	Circadian rhythm sleep disorder	Shift work disorder	
	Delayed sleep phase	Sleep disorder due to general medical condition, insomnia type	
	Dyssomnia	Sleep disorder due to general medical condition, mixed type	
	Early morning awakening	Terminal insomnia	
	Fatal familial insomnia	Dysfunctions associated with sleep stages or arousal from sleep	
	Hyposomnia	Dyssomnia NOS	

	Initial insomnia	Jet lag
	Insomnia	Microsleep
	Insomnia exacerbated	Sleep deficit
	Insomnia NEC	Sleep disorder
	Insomnia related to another mental condition	Sleep disorder due to a general medical condition
	Irregular sleep phase	Sleep disorder NOS
	Irregular sleep wake rhythm disorder	Sleep disorder therapy
	Middle insomnia	Sleep inertia
Non-24-hour sleep-wake disorder		Sleep study abnormal
	Poor quality sleep	
FMQ Somnolence (broad)	Central nervous system depression NOS	Sedation aggravated
	Consciousness fluctuating	Somnolence
	Depressed level of consciousness	Somnolence neonatal
	Hypersomnia	Stupor
	Infant sedation	Altered state of consciousness
	Lethargy	Fatigue
	Neonatal oversedation	Fatigue aggravated
	Primary hypersomnia	Prostration
	Sedation	Sluggishness

An overall summary of adverse events will be presented, including frequency of schizophrenia relapse. The frequency of subjects with AEs will be summarised by treatment, primary system organ class (SOC) and preferred term (PT). The SOCs will be sorted by default in descending frequency and PTs will be sorted in descending frequency within an SOC in the iclepertin arm. Separate tables will be provided for patients with

- Related AEs
- Serious AEs
- Serious related AEs
- AESIs
- Other significant AEs
- AEs leading to death
- AE leading to discontinuation of trial medication
- AEs occurred with incidence in the preferred term >2%
- AEs suggestive of abuse potential or related to CNS depressant effects
- AEs in user-defined AE categories
- AEs occurred during the follow-up period.

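### The SAP's Drowsiness term list (Table 7.8.1: 3) does not contain Somnolence, so a patient whose only relevant event is coded Somnolence is not counted in that descriptive row

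*SAP*

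**What the plan says.** The Drowsiness subsection of SAP Section 7.8.1 gives one sentence of definition: "Drowsiness will be analyzed by a customized query defined in Table 7.8.1: 3". Table 7.8.1: 3 then lists preferred terms with a narrow or broad scope. The narrow terms are Depressed level of consciousness, Post-injection delirium sedation syndrome, Radiation somnolence syndrome and Sedation. The 15 broad terms range from Altered state of consciousness and Lethargy to Concussion, Intracranial hypotension and Shift work disorder. Somnolence appears in neither scope, and no reason is given.

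The same SAP section lists Somnolence in two other groupings: CNS depressant effects (Table 7.8.1: 1) and "FMQ Somnolence (broad" (Table 7.8.1: 4; closing bracket not included in the quote). The counting rule is "All analyses of AEs will be based on the number of subjects with AEs and not on the number of AEs". The list of planned tables includes one for "AEs in user-defined AE categories".

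In Protocol Table 1.4.2:1 the first risk entry begins "The most frequent AEs were CNS-related". One of its items is "Somnolence (drowsiness", the second word standing in brackets as a gloss on the first. Protocol Section 1.2, on clinical data to date, says: "Dizziness, somnolence and gastrointestinal disorders, such as nausea and vomiting, were also among the AEs reported more frequently on Iclepertin than placebo".

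**The concern.** A category called Drowsiness would be expected to include the general term that the sponsor's own risk table explains as drowsiness. The list instead includes one rare, specific form, "Radiation somnolence syndrome", as a narrow term. It also admits some distant conditions as broad terms, yet omits the general term. The omitted term is one that earlier studies showed more often on active drug.

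If the table is complete and is followed as written, the row undercounts patients in the category it names. It could also disagree with the FMQ Somnolence row for no stated reason. A reader who looks up the risk under the protocol's word would find the less complete of the two rows.

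**Working it through.** The plan states no figure on this point, so there is nothing to reproduce. The check is one of list membership, followed by an illustration under a stated assumption.

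**Step 1: count and membership.** The three lists were transcribed from SAP Section 7.8.1 and compared term by term.

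| Grouping | Terms | Contains Somnolence | Terms shared with Drowsiness |
|---|---|---|---|
| Drowsiness (Table 7.8.1: 3) | 4 narrow + 15 broad = 19 | No | – |
| FMQ Somnolence, broad (Table 7.8.1: 4) | 18 | Yes | 5 |
| CNS depressant effects (Table 7.8.1: 1) | 9 | Yes | 3 |

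The five terms shared with the FMQ list are Altered state of consciousness, Consciousness fluctuating, Depressed level of consciousness, Lethargy and Sedation. The last three of these are also the terms shared with CNS depressant effects. Only one Drowsiness term contains the word somnolence, namely Radiation somnolence syndrome, which is a different preferred term.

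**Step 2: apply the counting rule.** Events are counted by subject. A patient whose only relevant event is coded Somnolence contributes:

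- 0 to Drowsiness, whether narrow or broad;
- 1 to FMQ Somnolence (broad);
- 1 to CNS depressant effects;
- 1 to the Somnolence line of the table by system organ class and preferred term.

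A patient who has Somnolence and also a listed term, such as Sedation or Lethargy, is still counted under Drowsiness. The shortfall is therefore the number of patients with Somnolence and no listed term, not everyone with Somnolence.

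**Step 3: size.** The documents give no somnolence rate, so the shortfall cannot be derived from them. As an assumption only, let *p* be the share of an arm with Somnolence and no listed term, and take the planned arm of 293 from Protocol Section 7.5. Shortfall = *p* × 293:

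- *p* = 1%: 0.01 × 293 = 2.9, about 3 patients
- *p* = 2%: 0.02 × 293 = 5.9, about 6 patients
- *p* = 5%: 0.05 × 293 = 14.7, about 15 patients

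The base of 293 is the planned number randomised per arm. Adverse events are analysed on the Treated Set, whose size is not known in advance.

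**The case against.** The strongest objection is that the row may have been lost when the PDF was read. The narrow terms run alphabetically and end at Sedation, close to where Somnolence would come. The last broad terms are slightly out of order, and the neighbouring Table 7.8.1: 4 shows a column shift. None of this proves a loss: every row of Table 7.8.1: 3 has both a term and a scope, and no gap is visible. But a loss cannot be excluded from the text available. This part of the objection stands, and it is why the first step of the fix is to look at the original table.

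A second objection is that nothing is lost from the safety report. Somnolence is captured in two other groupings and under its own preferred term, Drowsiness is not an adverse event of special interest, and Protocol Section 7.2.5 plans no hypothesis testing for safety. This is correct and limits the consequence to one row. It does not make that row right.

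Third, the intent of the query is not documented. The protocol's wording is a gloss in a risk table, not a definition of this category, and one specific syndrome in the list does not fix the query's scope. Hypersomnia, present in both other groupings, is also absent, which could point to a deliberate division of terms or to more than one lost row. That is fair as to intent, but the SAP states no such division. Five terms appear in both the Drowsiness and FMQ lists, so the two categories are not kept separate in any case. The absence of Hypersomnia neither explains nor justifies leaving out Somnolence.

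Finally, the 1% to 5% range has no source in the documents, and the SAP does not say whether narrow and broad scopes will be shown separately or combined. Both points are accepted. The figures illustrate scale and are not an estimate.

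**Conclusion.** The concern holds, as a minor point. As the SAP reads, the only definition of Drowsiness omits the term that the protocol itself explains as drowsiness. Following the list as written would leave out any patient whose sole relevant event is coded Somnolence. This rests on the table being complete as read, which can only be settled against the original document; confidence is therefore medium. The undercount is not computable from the documents, and the 3 to 15 patients per planned arm depend entirely on the assumed 1% to 5%. No other row, endpoint or inference is affected.

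**What to change.** Before treatment information is released (SAP Section 8), compare Table 7.8.1: 3 with the original SAP. If a Somnolence row is there, nothing further is needed. If it is not, either add Somnolence with its narrow or broad scope, or add a sentence explaining why it is left out of Drowsiness while being counted in the other two groupings.

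The cost is one check of one table and, at most, one added preferred term or one sentence. Doing this before unblinding avoids a post hoc change to a safety category.

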### Sleep disorder

Sleep disorder related AE search terms are based upon the FDA Medical Queries (FMQs) of Insomnia (broad) and Somnolence (broad). Refer to Table 7.8.1: 4 for a list of MedDRA preferred terms in each of the groupings.

Table 7.8.1: 4 MedDRA preferred terms for user-defined AE categories of sleep disorder AEs

User-defined AE category	MedDRA preferred terms		
FMQ Insomnia (broad)	Advanced sleep phase	Primary insomnia	
	Behavioural induced insufficient sleep syndrome	Psychophysiologic insomnia	
	Circadian rhythm sleep disorder	Shift work disorder	
	Delayed sleep phase	Sleep disorder due to general medical condition, insomnia type	
	Dyssomnia	Sleep disorder due to general medical condition, mixed type	
	Early morning awakening	Terminal insomnia	
	Fatal familial insomnia	Dysfunctions associated with sleep stages or arousal from sleep	
	Hyposomnia	Dyssomnia NOS	

	Initial insomnia	Jet lag
	Insomnia	Microsleep
	Insomnia exacerbated	Sleep deficit
	Insomnia NEC	Sleep disorder
	Insomnia related to another mental condition	Sleep disorder due to a general medical condition
	Irregular sleep phase	Sleep disorder NOS
	Irregular sleep wake rhythm disorder	Sleep disorder therapy
	Middle insomnia	Sleep inertia
Non-24-hour sleep-wake disorder		Sleep study abnormal
	Poor quality sleep	
FMQ Somnolence (broad)	Central nervous system depression NOS	Sedation aggravated
	Consciousness fluctuating	Somnolence
	Depressed level of consciousness	Somnolence neonatal
	Hypersomnia	Stupor
	Infant sedation	Altered state of consciousness
	Lethargy	Fatigue
	Neonatal oversedation	Fatigue aggravated
	Primary hypersomnia	Prostration
	Sedation	Sluggishness

An overall summary of adverse events will be presented, including frequency of schizophrenia relapse. The frequency of subjects with AEs will be summarised by treatment, primary system organ class (SOC) and preferred term (PT). The SOCs will be sorted by default in descending frequency and PTs will be sorted in descending frequency within an SOC in the iclepertin arm. Separate tables will be provided for patients with

- Related AEs
- Serious AEs
- Serious related AEs
- AESIs
- Other significant AEs
- AEs leading to death
- AE leading to discontinuation of trial medication
- AEs occurred with incidence in the preferred term >2%
- AEs suggestive of abuse potential or related to CNS depressant effects
- AEs in user-defined AE categories
- AEs occurred during the follow-up period.

### 7.8.2 Laboratory data

The analyses of laboratory data will be descriptive in nature and will follow BI standards (4).

Descriptive statistics for laboratory values will be displayed using the converted values in standard unit for data analyzed by the central laboratory. Shift tables of change in laboratory measurements between baseline and minimum, maximum or last value on treatment will be presented.

Page 41 of 54 c45059945-01

Proprietary confidential information © 2024 Boehringer Ingelheim International GmbH or one or more of its affiliated companies

Data in the post-treatment period will also be summarized.

### 7.8.3 Vital signs

Only descriptive statistics are planned for this section of the report.

### **7.8.4** ECG

Clinically relevant abnormal ECG findings will be reported and analysed as AEs.

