5.2.4 Electrocardiogram

The 12-lead ECGs will be performed as scheduled in the Flow Chart. Twelve-lead ECGs (I, III, aVR, aVL, aVF, V1 – V6) will be recorded using equipment provided by a central ECG vendor. The ECGs will be recorded for at least 10-second duration after the patients have rested for at least 5 minutes in a supine position and prior to lab sampling. Electrode placement will be performed according to the method of Einthoven/Goldberger (ankles and wrists). At all-time points indicated in the Flow Chart, single ECGs will be recorded. ECG recordings at planned time points may be repeated for quality reasons like alternating current artefacts, muscle movements and electrode dislocation. In this case the repeated ECG recordings will be used if quality was better.

The investigator or a designee will evaluate whether the ECG is normal or abnormal and whether it is clinically significant, if abnormal. The electronic version of the ECG is regarded as source data. Dated and signed printouts will be stored in the patient's medical file if there is no validated and certified e-medical record for ECG data.

Additional ECGs may be collected by the investigator for safety reasons. Clinically relevant findings noticed at Visit 1 should be reported as baseline condition.

Clinically relevant abnormal findings noticed after Visit 1 will be reported as an AEs and followed up and/or treated locally until normal or stable condition.

All ECGs will be transmitted electronically to the central ECG vendor for centralized and independent evaluation. The vendor will provide a report to the site. Abnormalities detected during this centralized ECG evaluation will not necessarily qualify as an AE. Decisions on eligibility for the trial are the responsibility of the investigator. Abnormalities detected in central evaluation must be reviewed by the investigator and if considered clinically significant reported as Baseline condition if identified at visit 1 or as an AE, if identified at or after Visit 2. All clinically relevant abnormal findings will be managed as medically appropriate, per investigators clinical judgment.

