5.7 APPROPRIATENESS OF MEASUREMENTS

All measurements performed during this trial are accepted measurements that are commonly used in monitoring safety aspects or assessing treatment response in patients with CIAS.

The scheduled measurements are appropriate to see drug induced changes in physical examination, vital signs, ECG and standard laboratory values. The primary and secondary efficacy endpoints and safety endpoints are standard and accepted for evaluation of safety and tolerability of an oral drug, and they are widely used in these kind of studies. The period of 26 weeks of treatment with Iclepertin is deemed appropriate to see a change in cognitive function in schizophrenic patients.

Therefore, the appropriateness of all measurements applied in this trial is given.

Page 69 of 112

Proprietary confidential information © 2023 Boehringer Ingelheim International GmbH or one or more of its affiliated companies

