7.2.5 Safety analyses

AEs will be coded using the Medical Dictionary for Drug Regulatory Activities (MedDRA). Standard BI summary tables and listings will be produced.

All treated patients will be included in the safety analysis and will be summarized under the actual trial medication received at randomization. In general, safety analyses will be descriptive in nature and will be based on BI standards. No hypothesis testing is planned.

Statistical analysis and reporting of AEs will concentrate on treatment-emergent AEs. To this end, all AEs occurring between the start of treatment and the end of the REP will be considered 'treatment-emergent'. The REP is defined as 12 days after the last dose of trial medication. AEs that start before first drug intake and deteriorate under treatment will also be considered as 'treatment-emergent'.

Frequency, severity, and causal relationship of AEs will be tabulated by system organ class and preferred term after coding according to the current version of the MedDRA.

Frequency tables for all AEs, protocol-specified AESI, SAE, AE leading to death, AE leading to discontinuation, investigator assessed drug-related AE and serious related AE will be generated for treatment-emergent AEs. In addition, summary statistics and descriptive analyses will be conducted for other safety parameters that are assessed using dedicated scales, including suicidality as assessed by C-SSRS, disease severity as assessed by total score and changes over time on AIMS, SAS and BARS scales for EPS and related movement impairments.

Laboratory data will be analysed both quantitatively as well as qualitatively. The latter will be done via comparison of laboratory data to their reference ranges. Values outside the reference range as well as values defined as clinically relevant will be highlighted in the listings. Treatment groups will be compared descriptively with regard to distribution parameters as well as with regard to frequency and percentage of patients with abnormal values or clinically relevant abnormal values.

Vital signs, physical examinations, or other safety-relevant data observed at screening, baseline, during the course of the trial and at the end-of-trial evaluation will be assessed with regard to possible changes compared to findings before start of treatment.

Withdrawal-related safety analysis

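### SAP 7.8.4 brings ECGs into the analysis only through investigator-reported AEs, so no visible planned analysis compares centrally evaluated ECGs between arms or with pre-treatment findings

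*SAP*

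**What the plan says.** **SAP.** Section 7.8.4 reads in full: "Clinically relevant abnormal ECG findings will be reported and analysed as AEs". The neighbouring sections do more. Section 7.8.3 plans descriptive statistics for vital signs. Section 7.8.2 plans descriptive statistics and baseline-to-on-treatment shift tables for laboratory data. Section 4, which lists changes from the protocol's planned analysis, does not mention ECG.

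**Protocol, analysis.** Section 7.2.5 covers vital signs, physical examinations, "or other safety-relevant data observed at screening, baseline, during the course of the trial" and at the end of the trial. These data "will be assessed with regard to possible changes compared to findings before start of treatment". ECG is not named in that sentence.

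**Protocol, purpose.** Section 5.7 does name it: "The scheduled measurements are appropriate to see drug induced changes in physical examination, vital signs, ECG and standard laboratory values".

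**Protocol, collection.** The Flow Chart schedules a 12-lead ECG at Visits 1, 2, 5 and 8, at EOT or eEOT, and at Follow-up 2, 4 and 6. These are the same visits as for vital signs. Section 5.2.4 states: "All ECGs will be transmitted electronically to the central ECG vendor for centralized and independent evaluation". It adds that "Abnormalities detected during this centralized ECG evaluation will not necessarily qualify as an AE". The investigator must review central abnormalities, and those judged clinically significant are recorded as a baseline condition (Visit 1) or as an AE (from Visit 2). For the investigator's own reading the same section says: "Clinically relevant abnormal findings noticed after Visit 1 will be reported as an AEs".

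**The concern.** An ECG result enters the planned analysis only if an investigator judges it clinically significant and records an AE. That filter suits individual patient safety but is a poor way to compare arms. A moderate average change, or an excess of abnormal readings that investigators dismiss one by one, leaves few or no AEs.

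The randomised comparison is the informative one here. Every patient takes one or two antipsychotics, so single abnormal tracings are hard to attribute, whereas a difference between arms is not. The trial collects ECGs before, during and after treatment and has them evaluated centrally, yet the visible SAP specifies no by-arm use of those evaluations. At stake is whether the report can show that there was no ECG change over 26 weeks, or can only show that few ECG-related AEs were reported.

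**Working it through.** The plan states no figure for ECG, so there is none to reproduce. The check compares the texts and then gives an illustration.

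**Step 1: the same visits, three treatments of the data**

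| Data | Scheduled visits | Planned analysis in the visible SAP |
|---|---|---|
| Vital signs | 1, 2, 5, 8, EOT/eEOT, Follow-up 2, 4, 6 | Descriptive statistics (7.8.3), visit windows (6.7) |
| Laboratory | More frequent | Descriptive statistics, shift tables (7.8.2), visit windows (6.7) |
| ECG | Same as vital signs | AEs only (7.8.4) |

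Tables 6.7:4 to 6.7:6 are not visible in the SAP, so the absence of an ECG visit window cannot be relied on. Section 7.8.4 itself reads as complete.

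**Step 2: does another provision fill the gap?** Protocol 7.2.5 mentions standard sponsor tables and listings, but directly after AE coding. SAP section 9 cites sponsor guides for AEs, laboratory data and PK, and none for ECG. Neither document says that ECG parameters are covered by these standards or by the DMC's review.

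**Step 3: how much data is involved.** Eight scheduled ECGs for each of 586 patients gives 8 × 586 = 4,688 if every randomised patient completes. Protocol 7.5 projects that 30% to 40% will stop treatment early. Of the eight, two precede dosing (Visits 1 and 2) and three are on treatment (Visits 5, 8 and EOT). The three follow-up ECGs come at least 14 days after the last dose, past the 12-day residual effect period. The count describes what is collected, not what is lost.

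**Step 4: illustration of what each route can show.** The shift, threshold and reporting share are assumptions, because the documents give no ECG mean or SD. Arm sizes come from Protocol 7.5: n = 293 randomised and n = 220 evaluable. Safety analyses are descriptive, so power (two-sided 0.05) serves here only as a measure of visibility.

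*By-arm comparison of change, in SD units.*
- 95% CI half-width = 1.96 × √(2/n): 0.16 SD at n = 293 and 0.19 SD at n = 220.
- Power for a shift d = Φ(d√(n/2) − 1.96). For d = 0.3 and n = 293: Φ(3.63 − 1.96) = Φ(1.67) = 95%. For n = 220: Φ(3.15 − 1.96) = Φ(1.19) = 88%.

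*AE route.* Suppose a finding is clinically significant when it lies c SD above the mean, and a share r of such findings is reported.
- p₀ = r[1 − Φ(c)] and p₁ = r[1 − Φ(c − d)].
- Power = Φ((p₁ − p₀ − 1.96·SE₀)/SE₁), where SE₀ = √(2p̄(1 − p̄)/n), p̄ is the mean of p₀ and p₁, and SE₁ = √([p₀(1 − p₀) + p₁(1 − p₁)]/n).
- Most favourable case, c = 2, r = 1, d = 0.3, n = 293: p₀ = 0.0228 and p₁ = 0.0446, so 6.7 patients on placebo against 13.1 on iclepertin. Power = Φ((0.0218 − 1.96 × 0.0149)/0.0149) = 31%.
- Least favourable case, c = 3, r = 0.25: 0.1 against 0.3 patients, power about 4%.
- For d = 0.5 the same ranges of c and r give about 7% to 73%.

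The normal approximation is rough at such small counts. The contrast does not depend on its precision.

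**The case against.** The strongest reply is that the SAP follows the protocol section written for ECGs. Protocol 5.2.4 records clinically relevant findings as baseline conditions or AEs, requires the investigator to review central abnormalities, and so already separates pre-treatment from later findings. AEs are then tabulated by arm under SAP 7.8.1. Most of this stands. A reader might infer that the SAP breaks an explicit promise to analyse ECG change. The documents do not support that: 7.2.5 reaches ECG only through a catch-all phrase and specifies no statistic, and SAP 7.8.4 agrees with 5.2.4. But 5.2.4 governs collection and reporting and does not say that ECG is exempt from the assessment in 7.2.5. Section 5.7 gives ECG a purpose that AE counts serve poorly.

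A reader might also infer that an ECG effect would go unseen. That is too strong. An independent DMC reviews unblinded safety data, standard tables may exist, and an effect large enough to produce clinically significant findings can surface as AEs.

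Two further points stand. Protocol 1.2 reports no clinically relevant ECG findings in clinical studies so far, which lowers the priority, although the patient trials lasted 12 weeks against 26 here. And the documents mention only a vendor report to the site. They do not say that numeric intervals reach the sponsor, whereas Protocol 5.2.3 says so for laboratory results.

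**Conclusion.** The concern holds as a gap in the plan, of minor weight. No analysis in the visible SAP compares centrally evaluated ECGs between arms or with pre-treatment findings, so a shift that investigators do not judge clinically significant would not be shown by any planned analysis. This falls short of Protocol 7.2.5 and 5.7 without contradicting 5.2.4.

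Its size cannot be taken from the documents. The illustration (95% against 4% to 31% for a 0.3 SD shift at 293 per arm) rests on an assumed shift, threshold and reporting share, and shows only the direction and rough scale of the loss. The figure of 4,688 ECGs should not be read as its size: it is a total that assumes no early discontinuation and includes recordings outside treatment. The conclusion also assumes that the parts of the SAP not visible contain no ECG summary.

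**What to change.** In SAP 7.8.4, before unblinding:

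- Keep the AE reporting.
- Add a by-arm shift table of ECG evaluation (normal, abnormal, clinically significant) from baseline to the worst and to the last on-treatment value, with an ECG visit window if none exists.
- If the vendor's numeric measurements are available to the sponsor, add by-arm, by-visit descriptive statistics with change from baseline, and an outlier table with limits pre-set by the sponsor.

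If ECG is deliberately limited to AEs, say so in SAP section 4 and give the reason.

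The cost is extra programming and possibly a vendor data transfer. Confirm first that the data can be obtained, because the documents do not say. No new patient procedure is needed.
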